Postprandial lipemia is highly prevalent even in T2DM patients with normal fasting TG concentrations. Intestinal overproduction of chylomicrons (CMs) and the structural protein apolipoprotein (apo)-B48 has been identified as an integral feature of postprandial lipemia in T2DM and insulin resistance [3,4]. Each CM particle contains one apo-B48 molecule that remains the integral part of CM remnant particles during the lipolysis of the particles by LPL. Consequently apo-B48 can be utilized in vivo to track the secretion and metabolic fate of intestinally derived CM particles [5]. CMs contribute significantly but not exclusively to the elevation of postprandial triglyceride levels. Hepatic very low-density lipoprotein (VLDL) particles are quantitatively the major component leading to increased number of remnant particles.

We recently reported that elevation of plasma TG in abdominally obese dyslipidemic subjects at high CVD risk is due to dual metabolic defects; 1. overproduction of VLDL₁ particles linked to increased liver fat and subcutaneous abdominal fat, and 2. impaired catabolic rate of VLDL₁ particles associated with increases of

apo-CIII [6]. Our recent data suggest that the capacity of the lipolytic pathway is a determinant of both fasting and non-fasting triglyceride levels [7]. *Therefore it is clinically important to elucidate the mechanism for delayed postprandial lipemia and the interactions between dysglycemia and dyslipidemia in T2DM subjects.*

Incretins are hormones released from the gut that respond to the ingested nutrients and potentiate glucose-induced insulin secretion from the pancreatic β -cells. The most important incretins are glucagon-like peptide-1 (GLP-1) and glucose-dependent insulinotropic polypeptide (GIP), both of which are rapidly inactivated by the enzyme dipeptidyl peptidase-4 (DPP-4) [8-10]. Incretins are important in the regulation of postprandial glucose levels [11-13]. Importantly the incretin effect is strongly reduced or lost in T2 DM patients. Recently new approaches that targets incretin hormones including the GLP-1 receptor (GLP-1R) agonists and DPP4 inhibitors have been developed with a mechanism of action distinct from existing glucose lowering agents [10,14]. Incretin based therapies with GLP-1 agonists are accepted as an ideal add on therapy to intensify glucose control in combination therapy as they offer benefits like weight loss and no hypoglycemia [15].

[figure not shown]

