The study will be single blinded into two groups matched for age, sex and BMI in order to achieve similar weight loss in liraglutide and placebo arms. In addition to a fixed dose of metformin (2 g/day) and simvastatin (20 mg/day) treatments, patients will be assigned to liraglutide therapy once daily and randomized to liraglutide group with uncontrolled diet or to placebo group with weight loss of 3.0 kg supervised by the study dietician for 4 months (Figure 3). Previous studies in type 2 diabetes show that the average weight loss with liraglutide is 3-3.5 kg and stable weight is achieved within 3-3.5 months (LEAD1-6). The study cohort will comprise male and female (non-fertile or of child-bearing potential using a medically approved birth control method) with T2DM eligible for treatment with metformin or on stable dose of metformin.

INCLUSION CRITERIA

Obese subjects with T2D and a large waist (waist > 88 cm in women and > 92 cm in men, BMI 27–40 kg/m², triglycerides between 1.0 – 4.0 mmol/L and LDL < 4.5 mmol/l) treated with a lifestyle or metformin (any dose) (HbA1c 6.5-9%) and aged 30 – 75 years will be included. Subjects may or may not use statins. **Only subjects who sign an informed consent are included to the study.**

EXCLUSION CRITERIA

- Type 1 diabetes
- Apo E2/2 phenotype
- ALT/AST > 3x ULN
- GFR < 60 ml/min, clinically significant TSH outside normal range
- Lipid-lowering drugs other than statins within 6 months
- Treatment with pioglitazone, insulin, sulphonylureas, gliptines, glinides, SGLT-2 inhibitors or thiazide diuretics (at a dose of > 25 mg / day) within 6 months
- Blood pressure > 160 mmHg systolic and/or > 105 diastolic
- History of pancreatitis or stomach / other major bleeding, thyroid neoplasia, persistent hypothyroidism or persistent hyperthyroidism
- Any medical condition that puts the patient in the risk of dehydration
- Concurrent medical condition that may interfere with the interpretation of efficacy and safety data during the study.
- Females of childbearing potential who are not using adequate contraceptive methods
- Subjects who have experienced side-effects previously from GLP-1 agonists
- Non-compliance or withdrawal of consent
- **Any information or clinical event described in liraglutide SPC that is a contraindication for the use of liraglutide (http://www.ema.europa.eu/docs/en_GB/document_library/EPAR_-_Product_Information/human/001026/WC500050017.pdf)**

WHITHDRAWAL FROM THE STUDY

- Withdrawal of consent

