- Clinical information/condition/adverse event that potentially endangers study subject/study results judged by the PI of the study
- **any information or clinical event described in liraglutide SPC that is a contraindication for the use of liraglutide (http://www.ema.europa.eu/docs/en_GB/document_library/EPAR_-_Product_Information/human/001026/WC500050017.pdf)**

Restrictions during the study:

- No aspirin and non-steroidal anti-inflammatory drugs (NSAIDs) within 1 week before heparin tests (LPL / HL) and biopsies
- No alcohol or strenuous exercise within 72 hours of each special test
- Serum amylase and lipase is followed at screening, week 8 and end of liraglutide treatment period or at clinical suspicion of pancreatitis

STUDY VISITS

All subjects will undergo a screening visit. Before screening, the subjects may visit the study center for screening laboratory tests. After giving extensive oral and written information, a written informed consent form will be obtained from the subjects at the first visit before screening procedures. Subjects will be informed on all adverse events related to all the study procedures they will be submitted to both orally and in writing.

Subjects eligible for the study will enter the run-in phase and treated with Metformin 2 g/day and Simvastatin 20 mg/day for 4 weeks. In the treatment period, subjects are randomized to Liraglutide or placebo. To keep subjects blinded, Liraglutide and placebo will be visually identical and be packed. Liraglutide and placebo will be provided by Novo Nordisk A/S. Investigators are not blinded in order to advice subjects

in placebo group to lose weight 3 kg during the study. Dose will be escalated to Liraglutide 0.6 mg / placebo 0.1 ml for one week, Liraglutide 1.2 mg/ placebo 0.2 ml one week and thereafter Liraglutide 1.8 mg / placebo 0.3 ml s.c. daily injections.

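### No weight-stability criterion at entry, and only placebo has a weight target, so the intended weight match is unprotected against weight drift already present at entry

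*Combined protocol and SAP*

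**What the plan says.** **The weight match.** Under Treatment, the groups are "matched for age, sex and BMI in order to achieve similar weight loss in liraglutide and placebo arms", and patients are "randomized to liraglutide group with uncontrolled diet or to placebo group with weight loss of 3.0 kg supervised by the study dietician for 4 months". Placebo therefore has a number to reach and liraglutide has none. Study Visits adds that investigators are unblinded so that they can advise the placebo group on losing 3 kg. Research Hypothesis relies on the design to separate weight-dependent from weight-independent effects of liraglutide.

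**Entry.** Besides limits on waist, BMI, triglycerides and LDL, the Inclusion Criteria require that subjects are "treated with a lifestyle or metformin (any dose) (HbA1c 6.5-9%) and aged 30 – 75 years will be included". No condition concerns recent weight change. The Exclusion Criteria bar "Treatment with pioglitazone, insulin, sulphonylureas, gliptines, glinides, SGLT-2 inhibitors or thiazide diuretics (at a dose of > 25 mg / day) within 6 months". That list contains neither anti-obesity drugs nor GLP-1 agonists. A separate line excludes "Subjects who have experienced side-effects previously from GLP-1 agonists". The introductory text on incretins recommends GLP-1 agonists "as they offer benefits like weight loss and no hypoglycemia", so the protocol itself regards the class as weight-lowering.

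**Run-in.** Study Visits states: "Subjects eligible for the study will enter the run-in phase and treated with Metformin 2 g/day and Simvastatin 20 mg/day for 4 weeks". It sets no weight condition for going on to randomization.

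**Endpoints and analysis.** The second primary objective concerns hepatic de novo lipogenesis (DNL) and liver fat on liraglutide, judged against baseline. Statistical Methods and Power plans paired t-tests within group, an ANCOVA with unnamed covariates for the treatment effect, and 13 completers per arm.

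**The concern.** In most randomized trials, a weight trend shared by both arms cancels in the comparison. Here it need not. The placebo total is pulled toward a fixed 3.0 kg whatever the subject was doing beforehand, while on liraglutide any earlier loss or regain adds to the drug's effect. To the extent that the placebo target is met, a non-zero mean drift becomes a difference in weight loss between arms, and the weight-independent reading assumes that this difference is small.

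There is a second route, which does not depend on the placebo target. A subject whose weight is moving at baseline may also have liver fat, DNL and lipoprotein kinetics in motion. The before-after change on liraglutide then includes that movement, and a paired test has no control arm to remove it.

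**Working it through.** **Inputs from the documents:** placebo target 3.0 kg; expected average liraglutide loss 3 to 3.5 kg (Treatment); about 4 months of treatment; 13 completers per arm. **Not in the documents:** any drift figure. All drift values below are assumptions. A negative sign means losing weight.

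1. *The plan's own figures, with no drift.* Liraglutide loss minus placebo loss is 3.0 − 3.0 = 0 to 3.5 − 3.0 = 0.5 kg. That is the mismatch the design implies when everything goes as expected.

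2. *A few drifting subjects, all in one direction.* Shift in the liraglutide mean = m × d × 4 / 13, for m subjects drifting d kg/month.
   - m = 2, d = 0.5: 4/13 = 0.31 kg, or 10% of 3.0 kg
   - m = 3, d = 1.0: 12/13 = 0.92 kg
   - m = 4, d = 1.0: 16/13 = 1.23 kg, or 41% of 3.0 kg

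   For each m and d these are upper limits. They also assume that drift continues unchanged for 4 months, adds fully to the drug effect and is fully absorbed on placebo.

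3. *The same subjects with mixed directions.* Let each direction be equally likely. For m = 4, d = 1.0, all four agree in 2 of 16 sign patterns (1.23 kg), the net is two subjects in 8 of 16 (2 × 4/13 = 0.62 kg), and it is zero in 6 of 16. The mean absolute net count is (2×4 + 8×2 + 6×0)/16 = 1.5, so the mean absolute shift is 1.5 × 4/13 = 0.46 kg. For m = 2, d = 0.5, the shift is 0.31 kg half the time and zero otherwise.

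4. *A non-zero mean drift μ across the liraglutide arm.* Mismatch = (3 to 3.5) − 4μ − 3.0.

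| μ (kg/month) | Liraglutide loss minus placebo loss (kg) |
|---|---|
| −0.5 | 2.0 to 2.5 |
| −0.25 | 1.0 to 1.5 |
| 0 | 0 to 0.5 |
| +0.25 | −1.0 to −0.5 |
| +0.5 | −2.0 to −1.5 |

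5. *Drift with mean zero.* Only chance mismatch remains. The 95% range of the arm's mean drift is ±1.96 × 4 × SD/√13.

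| SD of drift (kg/month) | 95% range, liraglutide only | Chance of more than 1 kg either way | 95% range of the difference if both arms drifted freely |
|---|---|---|---|
| 0.25 | ±0.54 kg | <1% | ±0.77 kg |
| 0.5 | ±1.09 kg | 7% | ±1.54 kg |
| 0.75 | ±1.63 kg | 23% | ±2.31 kg |

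   The last column uses √(2/13) in place of 1/√13.

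6. *What an entry limit would admit.* A limit of L kg over 3 months admits a drift of L/3 kg/month, or 4L/3 kg over 4 months. For L = 3 that is 1.0 kg/month, or 4 kg over treatment, which is more than the 3.0 kg target and admits every subject in step 2.

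**The case against.** The strongest reply is that no drift is documented, so no mismatch is shown. A reader might infer that drift breaks the weight match, or that 0.31 to 1.23 kg is what to expect. The documents support neither. A systematic mismatch needs a non-zero mean drift, and mean-zero drift yields only the chance ranges in step 5. Steering placebo even narrows those ranges. Nor do the documents show that lifestyle-treated subjects have recently dieted; lifestyle is used there as a category of diabetes treatment.

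A reader might also infer that weight-lowering drugs are generally allowed. That is too broad. Current treatment is restricted to lifestyle or metformin, which rules out current GLP-1 agonist use, and SGLT-2 inhibitors are barred for 6 months. What remains open is anti-obesity drugs, and past GLP-1 agonist use that caused no side-effects.

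The common metformin run-in may look like a source of imbalance. All subjects receive it before randomization and the documents attach no weight effect to it. Its plainer bearing is on within-arm change.

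Study Visits provides a dietician meeting, weekly contacts about weight and diet, a week-8 weight, and an extra visit for unsuccessful loss or loss above 1.5 kg/month. None is limited to placebo, so liraglutide weight is watched. But these checks start after entry, the trigger tolerates 1.5 × 4 = 6.0 kg (twice the target), and it leads to a visit rather than to any stated weight goal on liraglutide.

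Finally, an entry rule cannot secure the match against other causes, since liraglutide weight loss is itself uncontrolled and no adjustment for weight change is specified. That is correct. It limits what the rule can achieve but does not remove the reason for having it.

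**Conclusion.** The gap is real and its harm is conditional. Nothing at entry protects the variable that the design tries to equate, and because only placebo has a target, randomization does not cancel a non-zero mean drift to the extent that the target is met. The liraglutide change from baseline in liver fat and DNL is exposed as well. The effect on those endpoints cannot be sized, because the documents do not link kilograms to liver fat or DNL.

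In weight terms, with 2 to 4 of 13 subjects assumed to drift 0.5 to 1.0 kg/month, the liraglutide mean moves by at most 0.31 to 1.23 kg, and by less with mixed directions. The upper end exceeds the 0 to 0.5 kg that the plan's own figures imply. This supports an inexpensive improvement to eligibility. It does not support a conclusion that the weight match fails.

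**What to change.** 1. Add to the Inclusion Criteria a requirement of stable weight before screening, rechecked with clinic weights at the start and end of the run-in. The sponsor sets the limit so that drift carried over 4 months is small against 3.0 kg. By step 6, 3 kg in 3 months is too loose. The run-in recheck needs its own stated limit.
2. Add anti-obesity drugs and GLP-1 agonists to the existing 6-month prior-treatment exclusion.

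The cost is the added eligibility text, two clinic weights, a few more screen failures and slightly slower recruitment.

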Thereafter the baseline visits will include an OGTT, heparin test, non-fasting kinetics and abdominal MRI investigation days. The investigational product (Liraglutide or placebo) will be given to the subjects together with detailed instructions about the usage and storage (**Shelf life 30 months. After first use: 1 month. Storage in a refrigerator (2°C - 8°C). Do not freeze. Store away from the freezer compartment.**) (in +2 - +8 degrees, opened product in +2 - +29 degrees) of the product during these visits. After the study period of total 4 months these investigations are repeated. In addition to the screening visit(s), the subjects will undergo 8 investigational visits. The subjects meet dietician after randomization. The follow-up about weight, diet and possible adverse events takes place with weekly phone calls/e-mail contacts by the study nurse/dietician/doctor. Subjects fill in dietary records for 3 days before and during the investigational drug. At week 8 after initiation of the treatment period a blood sample for safety is drawn, weight is recorded and the patient meets dietician/study nurse if necessary. In case of unsuccessful weight loss, weight loss > 1.5 kg/month or adverse events, an additional visit is arranged. The duration of the study is 1-1.5 month run in and 4 to 4.5 month investigational phase i.e. 5 to 6 months. The subjects will be followed by a phone call/e-mail/visit 2 weeks after the end of the treatment period.

STUDY PROTOCOL: We will combine the novel kinetic protocol developed by us with several advanced analyses to elucidate how incretins modulate postprandial lipidemia and hepatic DNL in T2D subjects. To specifically elucidate the impact of a GLP-1 agonist on postprandial lipid metabolism, we will perform kinetic studies on all study subjects before and after the 4-months intervention with the GLP-1 agonist.

[figure not shown]

Figure 4. Detailed schedule for lipoprotein kinetic assessment. Red dots represent plasma samples for kinetic data (glycerol, leucine and palmitate enrichment in TRL fractions) and green arrows illustrate time-points for plasma incretin (GLP-1, GIP), glucose and insulin sampling.

1. Kinetic study with stable isotopes combined with an oral fat load. This study is based on the novel protocol developed by us (Figure 4). A detailed description of analysis is given in **Appendix A**.

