The study continues until 13 subjects have completed in both arms. Subjects completing the protocol are included to the statistical analyses. Paired t-test (within group) and ancova (treatment effect) will be used. The number of subjects needed is based on previous studies and are in accordance with a recently published article showing that a 25% difference in VLDL kinetics can be detected with 9 subjects per each group [33].

PRIMARY OBJECTIVE

1) To examine the effect of 16 weeks of treatment with liraglutide on triglycerides (TG) and apoB48 production rates (PR) and/or fractional catabolic rates (FRC) in the lipoprotein fraction chylomicrons ($S_f > 400$) in patients with T2DM treated with metformin. This will be fulfilled by kinetic modeling during a standardized fat-rich mixed-meal test combined with stable isotope administration.

2) To evaluate the for the first time in humans the effect of 16 weeks of treatment with liraglutide compared to baseline on hepatic DNL and liver fat content in patients with T2DM treated with metformin, assessed during a standardized fat-rich mixed meal test.

SECONDARY OBJECTIVES

To evaluate the effect of 16 weeks of treatment with liraglutide compared to baseline in patients with T2DM treated with metformin, assessed during a standardized fat-rich mixed-meal test combined with stable isotope administration on:

- production rates (PR) of TG, apo-B48 and apo-B100 in the lipoprotein fractions VLDL₁ (Sf 60–400) and VLDL₂ (Sf 20–60)
- fractional catabolic rates (FCRs) of TG, ap-B48 and apo-B100 in the lipoprotein fraction VLDL₁ (Sf 60–400) and VLDL₂ (sf 20–60)
- fasting and postprandial serum total TG, total cholesterol, and total apo-B, apo-B48, RLP-chol and RLP-TG, apo-CIII and apo-A5 as well as fasting LDL and HDL size. RLP-chol and RLP-TG are surrogate markers of remnants. Apo-CIII and apo-A5 are key regulators of the lipolytic cascade.
- TRL clearance assessed as effect on post-heparin lipoprotein lipase (LPL) and hepatic lipase (HL) activities. LPL and HL are the key enzymes regulating lipolysis of TRLs and remnant removal by the liver.
- fasting and postprandial glucose, insulin and C-peptide, assessed also during an OGTT.
- fasting visceral and subcutaneous fat depots assessed by MRS in both fasting and in postprandial period.

SAFETY REPORTING

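### The six-month prior-treatment exclusion leaves out GLP-1 receptor agonists, so a recent, tolerant former user of the class under test could enter and may bring a partly treated baseline

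*Combined protocol and SAP*

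**What the plan says.** All references are to the combined protocol and SAP.

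- **Exclusion Criteria, prior treatment.** The bullet reads "Treatment with pioglitazone, insulin, sulphonylureas, gliptines, glinides, SGLT-2 inhibitors or thiazide diuretics (at a dose of > 25 mg / day) within 6 months". Gliptins, the other incretin-based class, are listed. GLP-1 receptor agonists are not.
- **Exclusion Criteria, prior GLP-1 use.** The only bullet that names the class is "Subjects who have experienced side-effects previously from GLP-1 agonists". It has no time window and says nothing about tolerated use.
- **Inclusion Criteria.** Entrants are people "treated with a lifestyle or metformin (any dose) (HbA1c 6.5-9"%). This describes therapy at entry and gives no look-back.
- **Study Visits, run-in.** "Subjects eligible for the study will enter the run-in phase and treated with Metformin 2 g/day and Simvastatin 20 mg/day for 4 weeks". Later in the same section: "The duration of the study is 1-1.5 month run in and 4 to 4.5 month investigational phase".
- **Primary Objective, item 2.** The aim is to evaluate "the effect of 16 weeks of treatment with liraglutide compared to baseline on hepatic DNL and liver fat content". The Secondary Objectives are also framed against baseline.
- **Statistical Methods and Power.** "Paired t-test (within group) and ancova (treatment effect) will be used", with 13 completers per arm.

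**The concern.** The plan requires six months off gliptins but sets no interval for the class it is testing. The background text treats the intestinal lipid effect as common to incretin-based drugs, so whatever reason there was to list gliptins applies at least as well to GLP-1 receptor agonists.

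A person who took such a drug without trouble and stopped shortly before screening could satisfy the written criteria. A person who stopped a gliptin on the same day could not. If some drug effect remains at the baseline tests, baseline liver fat, DNL, weight or lipid kinetics are partly treated values, and the change measured on liraglutide understates the effect of starting from an untreated state. The comparison with baseline is the stated form of the second primary objective and of the secondary objectives. With 13 completers per arm, each such person is a visible share of the mean.

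**Working it through.** **1. Does any other provision close the gap?**

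- *Lifestyle-or-metformin criterion:* bars current users only.
- *Side-effect bullet:* removes intolerant former users only.
- *Exclusion for interfering medical conditions:* concerns conditions, not past drugs.
- *Product-label contraindications:* incorporated by link, so their content cannot be checked here.
- *Run-in:* adds 4 weeks (elsewhere 1 to 1.5 months) to whatever time off drug preceded screening. It may not cover every baseline test: Study Visits lists an OGTT among the baseline visits, while the OGTT paragraph of the Study Protocol section places it at screening.
- *Withdrawal clause:* lets the principal investigator withdraw someone whose clinical information could endanger the study results. This is discretionary and is not a screening rule.

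None of these sets a look-back for the class.

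**2. The plan's own figure.** The only effect size is a 25% difference in VLDL kinetics, said to be detectable with 9 per group. SD, alpha, power and design are not stated, so the 9 cannot be reproduced. Assuming two-sided 5% and 80% power, the implied SD is:

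- two-sample: 25 / [(1.960 + 0.842) × √(2/9)] = 18.9%
- paired (SD of change): 25 / [(1.960 + 0.842) / √9] = 26.8%

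The 25% is used below only as an illustrative effect.

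**3. Dilution of the within-arm change.** Let E be the true change from an untreated baseline, k the number of recent users among 13 liraglutide completers, and f the share of the effect still present at baseline. Neither k nor f is in the documents.

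Mean change = E × (1 − f × k/13), so dilution = f × k/13.

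| k | f = 0 | f = 0.5 | f = 1 | mean change if E = 25%, f = 1 |
|---|---|---|---|---|
| 0 | 0% | 0% | 0% | 25.0% |
| 1 | 0% | 3.8% | 7.7% | 23.1% |
| 2 | 0% | 7.7% | 15.4% | 21.2% |

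**4. Paired t-test power.** n = 13, two-sided 5%, E = 25%, f = 1, from the noncentral t with 12 degrees of freedom and noncentrality (mean change / SD) × √13. The SDs of change are assumptions chosen around the implied values in step 2.

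| SD of change | k = 0 | k = 1 | k = 2 |
|---|---|---|---|
| 18.9% | 0.99 | 0.98 | 0.96 |
| 25% | 0.91 | 0.86 | 0.80 |
| 30% | 0.79 | 0.72 | 0.65 |

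This takes full carry-over and ignores the extra variance from mixing users with non-users.

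**5. The between-arm contrast.** Suppose k users in each arm, full carry-over at baseline, and the residual effect gone by 16 weeks in those on placebo. A liraglutide user then changes by 0 instead of −E, and a placebo user drifts by +E:

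Contrast = −E × (13 − k)/13 − E × k/13 = −E.

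The change-score contrast is undiluted. With one user in the liraglutide arm only, it is 25 × 12/13 = 23.1%. With one in the placebo arm only, it is 25 × 14/13 = 26.9%. Randomisation leaves the direction to chance. If the residual effect outlasted 16 weeks on placebo, the contrast too would be diluted, by k/13; the documents do not say how long it lasts.

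**The case against.** The strongest reply is that the affected group is narrow and may be empty. Current users are out, and so are those who had side-effects. What remains is people who tolerated the drug, stopped anyway, did so recently, and still meet the HbA1c, triglyceride, BMI and waist limits. Nothing in the documents says that any are expected. This stands, and it is why the range starts at zero.

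A second reply concerns reversal. A reader might infer from the Treatment section, where "the average weight loss with liraglutide is 3-3.5 kg and stable weight is achieved within 3-3.5 months", that the effect takes equally long to fade, so that a four-week run-in must be too short. The documents do not support this. The sentence describes onset on treatment, and no passage gives an offset time for weight, liver fat, DNL or lipid kinetics.

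Third, a reader might infer that the randomised treatment effect is biased. Step 5 shows why that does not follow: under washout on placebo, equal numbers of users cancel, and unequal numbers arise by chance.

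Fourth, a reader might infer that the weight match between arms is compromised. One or two placebo subjects regaining 3 kg would move the arm mean by 3 × 1/13 = 0.23 kg or 3 × 2/13 = 0.46 kg. That assumes full regain despite dietician supervision, weekly contacts, a week-8 weight and an extra visit if weight loss fails.

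Blinding and tolerability add little. The arms already differ in dietary advice, which gives every subject a cue; the main outcomes are tracer kinetics and spectroscopy; and tolerability is not among the objectives.

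These replies limit the size of the problem. They do not supply the missing look-back.

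**Conclusion.** The point holds as a minor gap in the eligibility criteria. As written, they admit a tolerant recent former user of the test class while excluding a recent gliptin user, and neither the run-in nor the discretionary withdrawal clause closes the gap.

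The consequence is a possible dilution of the within-arm, compared-to-baseline results: 0% with no such user, up to 7.7% with one and up to 15.4% with two among 13. The upper values assume that the whole effect is still present at baseline; partial carry-over gives proportionally less. The between-arm ANCOVA is exposed mainly to added noise and chance imbalance. Confidence is high for the omission and low to moderate for its size, because the number of such users and the time course after stopping are both unknown.

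**What to change.** Add GLP-1 receptor agonists to the existing Exclusion Criteria bullet on treatment within six months, in line with gliptins. If the investigators prefer another interval, they should state it, justify it and reconcile it with that bullet and the Inclusion Criteria. Keep the side-effect bullet as a separate exclusion. Record prior GLP-1 receptor agonist use, with the stop date, at screening, so that any such subject can be identified in the analysis.

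The cost is a few words in an amendment, one extra item in the screening history and possibly an occasional extra screen failure. No new procedure is needed.

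### Investigators who know the arm may withdraw a randomised subject to protect the study results, and the completers-only analysis carries any arm-related removal into the between-arm comparison

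*Combined protocol and SAP*

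**What the plan says.** All places are in the combined protocol and SAP.

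- **Withdrawal from the study.** There are three grounds: withdrawn consent; "Clinical information/condition/adverse event that potentially endangers study subject/study results judged by the PI of the study"; and "any information or clinical event described in liraglutide SPC that is a contraindication for the use of liraglutide". Non-compliance is not among them.
- **Exclusion criteria.** One item reads "Non-compliance or withdrawal of consent". Non-compliance is not defined, and no time point is attached to it.
- **Study visits, blinding.** "Investigators are not blinded in order to advice subjects" in the placebo arm to lose 3 kg. A 4-week run-in on metformin and simvastatin comes before randomisation.
- **Treatment.** Subjects are "randomized to liraglutide group with uncontrolled diet or to placebo group with weight loss of 3.0 kg supervised by the study dietician". The stated purpose is similar weight loss in the two arms.
- **Study visits, follow-up.** Weight, diet and adverse events are followed weekly by staff contact. "In case of unsuccessful weight loss, weight loss > 1.5 kg/month or adverse events, an additional visit is arranged". The kinetic study and the MRI/MRS are done at baseline and repeated after 4 months.
- **Statistical methods and power.** Only subjects who complete the protocol are analysed, and the study continues until 13 have completed in both arms. The tests are a paired t-test within group and ANCOVA for the treatment effect.

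**The concern.** A withdrawal rule should not let someone who knows the allocation decide that a subject's data would harm the study. Here the second ground joins two different things: danger to the subject, which is a safety matter, and danger to the results, which is not. The second has no criterion, no example and no check made without knowledge of the arm.

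Two features of the plan make this matter more than it usually would. First, the arms are asked to do different things. The placebo arm has a supervised weight target and the liraglutide arm has no diet control, so what staff see as a problem case can differ by arm. Second, there is no safeguard downstream. A subject withdrawn early has no 4-month kinetic or liver-fat measurement, is not analysed, and is in effect replaced, because the study continues until 13 complete per arm. No later choice of analysis set can recover an outcome that was never measured.

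What is at stake is the between-arm contrast, which is meant to separate the effect of liraglutide from the effect of losing weight.

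**Working it through.** **1. The sections side by side.**

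| Situation after randomisation | Exclusion criteria | Withdrawal list | Study visits |
|---|---|---|---|
| Consent withdrawn | listed | listed | – |
| Non-compliance | listed, undefined | absent | – |
| Clinical finding, condition or event judged to endanger the results | – | listed, PI judgement | – |
| Unsuccessful weight loss | – | absent | additional visit |

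Read literally, non-compliance can bar entry but gives no authority to withdraw. Yet it shares a line with withdrawal of consent, which the withdrawal list repeats, so a site cannot tell whether the item is meant to apply after randomisation.

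**2. Which analyses are exposed.** The ANCOVA compares completers in the two arms, so selection in either arm reaches it. The paired test in the liraglutide arm uses only that arm's completers. Placebo removals leave it unchanged; removals from the liraglutide arm would not.

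**3. Illustration of size.** The plan gives no expected number of withdrawals, so there is no planned figure to reproduce.

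- From the plan: 13 analysed per arm.
- Assumed: 15 randomised to placebo; the 2 with the least weight loss withdrawn; liraglutide arm unselected; no true difference; unit SD; correlation r between weight loss and a better outcome; two-sided t-test at 5%.
- Standard error of the difference: sqrt(2/13) = 0.392 SD.
- Simulated mean shift (200,000 runs) at r = 1: 0.230 SD. The shift is proportional to r, so r = 0.5 gives 0.230 × 0.5 = 0.115 and r = 0.3 gives 0.230 × 0.3 = 0.069. Simulation gives 0.114 and 0.070.
- In standard errors: 0.114/0.392 = 0.29 and 0.070/0.392 = 0.18.

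| r | Shift (SD) | Rejections favouring placebo | Rejections favouring liraglutide | Total |
|---|---|---|---|---|
| none removed | 0 | 2.5% | 2.5% | 5.0% |
| 0.3 | 0.07 | 3.7% | 1.7% | 5.4% |
| 0.5 | 0.11 | 4.9% | 1.3% | 6.2% |

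**4. Sensitivity to the assumptions.** With 4 of 17 removed, the shift is about 0.12 SD (total about 6.2%) at r = 0.3 and 0.19 SD (about 8.0%) at r = 0.5. For scale, 13 per arm detects about 1.15 SD with 80% power (two-sided 5%, t-test), so a shift of 0.07 to 0.11 SD is about 6% to 10% of that (0.07/1.15 = 0.06; 0.11/1.15 = 0.10).

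The simulation uses an unadjusted t-test. Under the planned ANCOVA, the relevant correlation and SD are those left after covariate adjustment, which the documents do not give.

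**The case against.** The strongest case on the other side is that the plan already deals with the most worrying scenario. A reader might infer that a placebo subject who fails to lose 3 kg can simply be removed as non-compliant. The text does not say so: non-compliance is not a withdrawal ground, and the stated response to unsuccessful weight loss is an extra visit, with no restriction by arm. Nor is non-compliance out of place as an exclusion, since it can be judged during the 4-week run-in.

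The study-results wording is also tied to a clinical finding, condition or adverse event. It is naturally read as meaning an illness that would invalidate the kinetics, much like the exclusion for concurrent conditions that interfere with interpretation. Treating a missed weight goal as such a finding stretches the text.

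Finally, liraglutide subjects can also leave, for adverse events or SPC contraindications, so the net direction across arms cannot be stated.

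Most of this stands, and it limits the point to what the wording permits. It does not remove it. Clinical information is a broad term, the judgement is made with knowledge of the arm, no sentence says that a subject with poor weight loss must stay in, and the completers-only rule passes any removal into the result.

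**Conclusion.** The point holds as a permitted route to bias in the between-arm ANCOVA, together with an inconsistency between the exclusion, withdrawal and visit sections. It is not evidence that any subject was removed for this reason. That the PI is unblinded is read from the general statement about investigators.

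Size and direction are unknown. In the illustration the shift is about 0.07 to 0.11 SD and two-sided type I error about 5.4% to 6.2%. This rests on 2 of 15 placebo subjects being lost on weight loss alone, r of 0.3 to 0.5, no selection in the liraglutide arm, and an unadjusted test.

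Two stronger readings should be resisted. A reader might infer false-positive claims for liraglutide, but in this scenario rejections favouring liraglutide fall from 2.5% to 1.3%–1.7%, so a real effect would tend to be masked. A reader might also take about 10.7%, the simulated total at r = 1, as the likely error rate; that would require weight loss to determine the endpoint completely, which is implausible. The liraglutide-versus-baseline comparisons are untouched by placebo removals.

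The change is still worth making, because it is cheap and the lost 4-month data cannot be recovered.

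**What to change.** 1. In the withdrawal section, remove danger to the study results as a ground for taking a randomised subject out of the study. Leave the safety and SPC grounds unchanged.
2. In the exclusion criteria, state that non-compliance applies only before randomisation, that is, during the run-in. Make this consistent with the visit section's response to unsuccessful weight loss.
3. State that a missed weight goal or other deviation after randomisation is recorded, and that the 4-month kinetic study and MRS already planned are done if the subject is willing and it is safe.
4. In the statistical section, include these subjects in the between-arm ANCOVA, and report withdrawals by arm and reason. The completer analysis can be kept as a sensitivity analysis. Without this step, a retained subject could still be left out as not having completed the protocol.

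These changes concern outcome collection and analysis only; they set no rule on stopping treatment. The cost is a few sentences, since the visits are already planned. The downside is slightly more noise from poorly adherent subjects.
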